Pharmacologie médicale

Bordeaux Pharmacoépi
CIC Bordeaux CIC1401

BROTHER

Benefit-Risk Of arterial THrombotic prEvention with Rivaroxaban
for atrial fibrillation in daily clinical practice.

A French cohort within the nationwide claims and hospital database

Protocol

Final version 1.0, 18 December 2015

Sponsor: Bayer Pharma AG

BORDEAUX PHARMACOEPI

Plateforme de recherche en pharmaco-épidémiologie
Service de Pharmacologie médicale, INSERM CIC1401
Université de BORDEAUX – CHU de Bordeaux – Adera
[name]
[name]

PASS INFORMATION

Title	Benefit-Risk Of arterial THrombotic prEvention with Rivaroxaban for atrial fibrillation in daily clinical practice. A French cohort within the nationwide claims and hospital database (BROTHER).
Protocol version identifier	Version 1.0
Date of last version of protocol	18 December 2015
IMPACT study number	18656
EU PAS register number	Study to be registered
Active substance	Rivaroxaban (ATC code B01AF01)
Medicinal product	Xarelto [®] 15 mg (CIP: 34009 219 225 1 6, 34009 219 226 8 4, 34009 219 227 4 5, 34009 219 228 0 6, 34009 581 416 7 6 Xarelto [®] 20 mg (CIP code: 34009 219 229 7 4, 34009 219 230 5 6, 34009 219 231 1 7, 34009 581 419 6 6,
Product reference	Xarelto [®] 15 mg: EU/1/08/472/011 to EU/1/08/472/016, EU/1/08/472/023, EU/1/08/472/036 Xarelto [®] 20 mg: EU/1/08/472/017 to EU/1/08/472/022, EU/1/08/472/024, EU/1/08/472/037
Procedure number	N/A
Marketing authorisation holder(s)	Bayer HealthCare AG
Joint PASS	No
Research question and objectives	The research question is to assess the one-year and two-year benefit-risk of rivaroxaban for stroke prevention in atrial fibrillation (SPAF) compared to vitamin K antagonists (VKA) and dabigatran among new anticoagulant users. The main objective is to compare the one-year and two-year risk of the following individual outcomes: Stroke and systemic embolism (SE), major bleeding and death, between new users of anticoagulant for SPAF during drug exposure: rivaroxaban versus VKA, and rivaroxaban versus dabigatran.
Country(-ies) of study	France
Author	[name] [name], Scientific and medical director Bordeaux Pharmacoépi (BPE), Service de Pharmacologie médicale, INSERM CIC1401 Université de Bordeaux – CHU de Bordeaux – Adera [name] [name] ☎ [name] - [contact] [contact]

MARKETING AUTHORISATION HOLDER(S)

2. LIST OF ABBREVIATIONS

ACS	Acute Coronary Syndrome
AF	Atrial Fibrillation
ANSM	French Medicines Agency (Agence Nationale de Sécurité du Médicament et des produits de santé)
BPE	Bordeaux PharmacoEpi, the Pharmacoepidemiology research platform of the University of Bordeaux - INSERM CIC1401
CIF	Cumulative Incidence Function
CHA ₂ DS ₂ -VASc	Risk score of stroke in patients with atrial fibrillation
CNAMTS	French national health insurance fund for salaried worker (Caisse Nationale de l'Assurance Maladie des Travailleurs Salariés)
CNIL	French data protection commission (Commission Nationale de l'Informatique et des Libertés)
CRB	Clinically Relevant Bleeding
DEP	Data Extraction Plan
DOAC	Direct Oral AntiCoagulants
DRG	Diagnosis-Related Groups (or GHM for Groupes Homogènes de Malades)
DVT	Deep Vein Thrombosis
EGB	1/97 random sample of the national health insurance database (Echantillon Généraliste de Bénéficiaires)
HAS	Haute Autorité de Santé
HAS-BLED	Risk score for predicting bleeding risk in anticoagulated patients with atrial fibrillation
hdPS	High-dimensional Propensity Score
IDS	Institute of Health Data (Institut des Données de Santé)
LTD	Long-Term Disease (registration for major chronic diseases with full insurance coverage of all claims related to disease)
MSA	French national health insurance fund for farmers and agricultural workers (Mutuelle Sociale Agricole)
MI	Myocardial Infarction
N	Number
NVAF	Non-Valvular Atrial Fibrillation
PE	Pulmonary Embolism (PE)
PMSI	National hospital discharge summary database (Programme de Médicalisation des Systèmes d'Information)
PY	Person-Years
RSI	French national health insurance fund for independent workers (Régime Social des Indépendants)
SAP	Statistical Analysis Plan
SNIIRAM	National healthcare insurance system database (Système National d'Information Inter-Régimes de l'Assurance Maladie)
SPAF	Stroke Prevention in Atrial Fibrillation
SPC	Summary of Product Characteristics
VKA	Vitamin K Antagonists
VTE	Venous Thromboembolic Events

4. ABSTRACT

TITLE Benefit-Risk Of arterial THrombotic prEvention with Rivaroxaban for atrial fibrillation in daily clinical practice. A French cohort within the nationwide claims and hospital database (BROTHER).

RATIONAL AND BACKGROUND Atrial fibrillation (AF) is an abnormal heart rhythm characterized by irregular beating. AF is associated with a five-fold increased risk of ischemic stroke, and accounts for up to 15% of strokes in persons of all ages and 30% in those over 80 years. Vitamin K antagonists (VKA) were the reference treatment for stroke prevention in AF (SPAF) and recommended for persons at increased risk of stroke.

Since 2012, three direct oral anticoagulants (DOAC), with a different mode of action from VKA, received a European market authorization for the prevention of stroke and systemic embolism in adult patients with non-valvular AF (NVAf) with one or more risk factors, such as congestive heart failure, hypertension, age \geq 75 years, diabetes mellitus, prior stroke or transient ischemic attack.

In France, Xarelto[®] (rivaroxaban 15 and 20 mg once daily) and Pradaxa[®] (dabigatran 110 and 150 mg twice daily) were launched in this indication in August 2012, and Eliquis[®] (apixaban 2.5 and 5 mg twice daily) in January 2014. The Transparency Committee of the HAS (*Haute Autorité de Santé*) gave a positive opinion for the reimbursement in this indication. As part of this procedure, the HAS requested Bayer to provide additional data documenting the therapeutic benefit of Xarelto[®] under actual conditions of use compared with the normal treatment of at-risk patients with NVAf.

In order to provide additional information to answer the HAS requests, especially the impact on morbidity and mortality, with a longer follow-up than for the NACORA studies, a rivaroxaban versus VKA comparison, as well as a face to face comparison between the two DOAC (rivaroxaban versus dabigatran), Bayer committed to a cohort study to be initiated about six months after the launch of the two first DOAC for SPAF using the national claims and hospitalisation database.

RESEARCH QUESTION AND OBJECTIVES **Research question:** To assess the one-year and two-year benefit-risk of rivaroxaban for SPAF compared to VKA and dabigatran among new anticoagulant users.

Main objective: To compare the one-year and two-year risk of each of the following individual outcomes: Stroke and systemic embolism (SE), major bleeding and death between new users of anticoagulant for SPAF during drug exposure: rivaroxaban versus VKA, and rivaroxaban versus dabigatran.

Secondary objectives:

- To describe the drug exposure to rivaroxaban, dabigatran, and VKA for SPAF in new users, as well as and pattern of use;
- To compare the one-year and two-year risk of the following individual outcomes: a composite of stroke and SE, major bleeding and death, clinically relevant bleeding (CRB) and acute coronary syndrome (ACS) between new users of anticoagulant for SPAF during drug exposure: rivaroxaban versus VKA, and rivaroxaban versus dabigatran;
- To estimate the cumulative incidence and the incidence rate of each

individual main and secondary outcome (stroke and SE, major bleeding, CRB, death, composite criteria, and ACS), as well as according to individual diagnose of each of these outcomes, during drug exposure for rivaroxaban, dabigatran, and VKA;

[figure not shown]
- To estimate the cumulative incidence of each individual main and secondary outcome (stroke and SE, major bleeding, CRB, death, composite criteria, and ACS), as well as according individual diagnose of each of these outcomes during post-anticoagulant exposure for rivaroxaban, dabigatran, and VKA (i.e. after anticoagulant discontinuation);
- To assess outcome risk factors, including (but not limited to), gender, age, stroke and bleeding risk scores (CHA₂DS₂-VASc and HAS-BLED), low or high dosage at index date for DOAC, drug predisposing to bleeding during drug exposure and significant baseline characteristics;
- To describe and compare healthcare resources utilisation related to SPAF during rivaroxaban, dabigatran, and VKA exposure, including outcomes, and their related costs from the societal perspective and from the French healthcare insurance perspective.

STUDY DESIGN A cohort study in a healthcare claims and hospitalisation database including new users of rivaroxaban, dabigatran, or VKA for SPAF with a follow-up for at least one year and up to two years per subject.

Data will be extracted from 1 January 2010 to 31 December 2015:

- The index date will be the first reimbursed dispensation of rivaroxaban, dabigatran, or VKA in 2013 or 2014, and without dispensation of any of them within the 3 years before index date.
- The study follow-up period will start on the study index date and will end two years later, or until the date of death with a right censoring on 31 December 2015 (at least a one-year follow-up period except for death).
- Rivaroxaban, dabigatran, or VKA exposure will be defined during the study follow-up period, as well as the occurrence of each of the study outcome.

The overall design of the study is presented in the following figure.

POPULATION Subjects with a first reimbursed dispensation of rivaroxaban (15 or 20 mg),

dabigatran (110 or 150 mg), or VKA in 2013 or 2014 and no previous anticoagulant dispensation during the previous three years, with a specific or sensitive diagnosis of non-valvular AF (NVAF). Two NVAF cohorts will be defined:

- Specific NVAF cohort (for the main analysis) will include definite NVAF subjects as defined below (to minimize the risk of false positives);
- Sensitive NVAF cohort (as secondary analysis) will include definite NVAF and probable NVAF subjects as defined below (to minimize the risk of false negatives).

Definite NVAF subjects: Definite AF information in the database, and no other indication for the use of anticoagulant (treatment of venous thromboembolic events (VTE), prevention of VTE after orthopaedic surgery), or history of rheumatic valve disease or valve replacement.

Probable NVAF subjects: Probable AF information in the database (using the development of an AF disease score), and no other indication for use of anticoagulant (treatment of VTE, prevention of VTE after orthopaedic surgery), or history of rheumatic valve disease or valve replacement.

VARIABLES

Disease definition

- Definite AF: Hospitalisation with an AF diagnosis (primary, linked or associated) or a procedure for AF (cardioversion, catheter ablation), or a Long-Term Disease (LTD) registration for AF in the 36 months before the index date or within six months after index date.
- Probable AF: Subjects without definite AF, and with anticoagulant and amiodarone or dronedarone co-prescription, or having a high probability of AF, using an AF disease score based on a logistic regression of the definite AF population with the following parameters (see statistical analysis):
 - Gender and age of the subject at index date,
 - Cardiologist or hospital physician prescriber of the first DOAC or VKA dispensation,
 - Investigation within 2 months before index date: Holter ECG monitoring or echocardiography, T3-T4 thyroid hormone test, D-dimer test or venous echo-doppler,
 - ≥ 1 drug dispensation within 3 months before index date for acetylsalicylic acid (ASA), ASA in association, clopidogrel, heparin or low-molecular-weight heparin (LMWH),
 - ≥ 1 drug dispensation within 2 months before or 2 months after index date of sotalol, other beta-blockers excluding associations, beta-blockers in association, verapamil or diltiazem, digoxin or digitoxin, other antiarrhythmic drug, other calcium channel blocker, agents acting on the renin-angiotensin system, diuretic.

Disease definitions for exclusion criteria

- Rheumatic valve disease (subjects excluded): Hospitalisation or LTD registration with rheumatic valve disease diagnosis, before index date (three-year history).
- Valve replacement (subjects excluded): Hospitalisation with diagnosis-related group of valve replacement or medical procedure for valve replacement (three-year history).
- Other probable indications of first anticoagulant dispensation (subjects excluded):
 - Treatment of VTE: index date within 2 months after hospital discharge

for pulmonary embolism or deep vein thrombosis;

- Prevention of VTE after orthopaedic surgery: index date within 2 months after hospital discharge for an orthopaedic surgery.

Exposure

- Treatment group: Defined by the first anticoagulant dispensation during the inclusion period, i.e. rivaroxaban high or low dosage, dabigatran high or low dosage, or VKA.
- Index date: Date of the first dispensation of anticoagulant in the treatment group.
- Duration of a drug dispensation will be defined as the number of daily doses for DOAC and 30 days for VKA;
- Drug exposure (rivaroxaban, dabigatran, or VKA): Period starting at the index date and ending at the date of the last drug dispensation plus the duration of the last drug dispensation for subject with a drug discontinuation or at the date of another anticoagulant dispensation (switch) or at the end of follow-up, whichever is the earliest.
- Drug (DOAC or VKA) discontinuation: with a grace period of 60 days for the main analysis and 30 days for a sensitive analysis after a “last” dispensation plus the duration of the last drug dispensation.
- Drug (DOAC or VKA) switch: Dispensation of another anticoagulant, including heparin and LMWH dispensation for subject with a drug discontinuation.
- Post drug (DOAC or VKA) exposure: Period starting at date of the end of drug exposure and ending at the date a new prescription of an anticoagulant or at the end of follow-up, whichever is the earliest.
- DOAC compliance: Estimated using Medication Possession Ratio (MPR) during drug exposure defined by the number of defined daily doses dispensed, divided by the number of days of drug exposure for DOAC.
- During a hospitalisation, drugs are provided by the hospital, and this time will be taken into account for calculation of drug exposure and drug discontinuation.

Outcomes

- Stroke and SE: Hospitalisation with one of the two following primary diagnoses:
 - Ischemic or undefined stroke,
 - Other systemic arterial embolism or surgical procedure for systemic arterial embolism.
- Major bleeding: Hospitalisation with one of the three following primary diagnoses:
 - Haemorrhagic stroke,
 - Other critical organ or site bleeding (intraspinal, intraocular, retroperitoneal, intraarticular or pericardial, or intramuscular),
 - Other bleeding with a transfusion during hospital stay, or resulting in death.
- Clinically relevant bleeding (CRB): Hospitalisation with one of the five following primary diagnoses:
 - Haemorrhagic stroke,
 - Other critical organ or site bleeding (intraspinal, intraocular, retroperitoneal, intraarticular or pericardial, or intramuscular),
 - Gastro-intestinal bleeding,
 - Urogenital bleeding,

- Other bleeding.
- Death: All-cause death.
- ACS: Hospitalisation with one of the two following primary diagnoses:
 - Myocardial infarction (MI),
 - Unstable angina.

Potential confounding

- Gender and age at index date,
- CHA2DS2-VASc score (stroke risk factor score) at index date: Sum of points from congestive heart failure (+1), hypertension (+1), age \geq 75 years (+2), diabetes mellitus (+1), stroke or transient ischemic attack history (+2), vascular disease history (+1), age 65-74 years (+1), female gender (+1),
- CHADS2 score (stroke risk factor score for descriptive analysis) at index date: Sum of points from congestive heart failure (+1), hypertension (+1), age \geq 75 years (+1), diabetes mellitus (+1), stroke or transient ischemic attack history (+2),
- HAS-BLED score (bleeding risk factor score) at index date: Sum of points from hypertension (+1), abnormal renal function (+1), abnormal liver function (+1), stroke history (+1), bleeding history (+1), age > 65 years (+1), drug predisposing to bleeding (+1),
- High dimensional Propensity Scores (hdPS) at index date for the probability of being treated by one of the studied drugs (rivaroxaban versus VKA, rivaroxaban versus dabigatran),
- Drug predisposing to bleeding during drug exposure: ASA, NSAIDs, antiplatelet agent and heparin or LMWH.

Healthcare resources

- Cardiovascular hospitalisations: Hospitalisations with primary diagnosis or diagnosis-related group of cardiovascular disease,
- Non-cardiovascular hospitalisations: Hospitalisations other than those defined above,
- Medical visits and technical acts,
- Cardiovascular and antidiabetic drugs reimbursed,
- Non-cardiovascular/antidiabetic drugs reimbursed,
- Lab tests,
- Products and services,
- Nursing acts,
- Physiotherapy acts,
- Transports,
- Sick leave daily allowances, disability allowances, pension,
- Other medical resources.

Healthcare resources related to AF

- Specific Hospitalisations: Hospitalisations with primary diagnosis of AF, or cardioversion, or catheter ablation procedure, or stroke or systemic embolism, or CRB,
- Specific drugs: DOAC, VKA, beta-blockers, amiodarone, dronedarone, other antiarrhythmics,
- Specific lab tests: INR, haemostasis tests, creatinine, creatinine clearance, ALAT, ASAT, including sampling,
- Specific medical visits: cardiologist visit, other medical visits with date

corresponding to the date of prescription of specific drugs or lab tests, neurologist visit after stroke event,

- Specific transport: Transport with date corresponding to the date of a specific hospitalisation, medical visit, medical procedure, or lab test.

Healthcare resources cost

- From a societal perspective: Diagnosis-related group cost for hospitalisations and total cost for other healthcare resources.
- From the French healthcare insurance perspective: Stay-related group cost for hospitalisations and reimbursed cost for other healthcare resources.

DATA SOURCES

The SNIIRAM database is the national healthcare insurance system database with individual anonymous information on all reimbursed outpatient claims linked to the national hospital-discharge summaries database system (PMSI) and the national death registry. It currently includes more than 96% of the French population of 65 million persons. To the extent that the SNIIRAM is a national database, all subjects are followed-up until they died, or for some people until they leave the country to live abroad. It contains individual anonymised information on:

- Demographic characteristics: gender, year of birth, area of residence;
- Date of death;
- Long-term disease (LTD and associated ICD-10 codes) registration for full insurance coverage (with start and end dates);
- Outpatient reimbursed healthcare expenditures with dates and codes (but not the medical indication nor result): visits, medical procedures, lab tests, drugs and medical devices, etc;
- Hospital-discharge summaries from PMSI: ICD-10 diagnosis codes (primary, linked and associated diagnoses) for all medical, obstetric and surgery hospitalisations, with the date and duration, medical procedures and cost coding system.

Access to SNIIRAM is regulated and needs approval from IDS (Institute of health data) and CNIL (French data protection commission). Hospital data are uploaded once a year and made available in the third quarter following the last year considered (i.e. the third quarter of 2016 for the extraction relating to the 2015 follow-up period).

STUDY SIZE

Using a previous study of VKA for SPAF, about 100 000 and 150 000 subjects are expected, respectively for the specific NVAF population and the sensitive NVAF population for a two-year inclusion period.

The number of subjects treated with rivaroxaban, dabigatran, and VKA, as well as the number of subjects who can be matched for each comparison (rivaroxaban versus VKA, rivaroxaban versus dabigatran) will be a result of the study, but it should be clearly higher than the 7 131 and 7 133 subjects randomized in the rivaroxaban and VKA arms of the ROCKET AF trial.

DATA ANALYSIS

A statistical analysis plan (SAP) will be developed and validated by the scientific committee before analysis. The statistical analysis will be performed using SAS[®] software (latest current version), following the SAP.

Probable AF will be estimated using AF disease score with a logistic regression model to predict AF diagnosis among subjects without history of rheumatic valve disease or valve replacement, or other probable indications, using variables defined above (see disease definition).

The probability to be treated by rivaroxaban or VKA, as well as rivaroxaban or dabigatran will be estimated with hdPS. The hdPS will be estimated using a logistic regression model with a large set of variables at index date and three-year history before inclusion, including gender, age, CHA2DS2-VASc and HAS-BLED scores.

For the rivaroxaban versus VKA comparison, subjects will be matched 1:1 on hdPS and index date within each population (specific and sensitive); For the rivaroxaban versus dabigatran comparison, subjects will be matched 1:1 on high or low DOAC dosage at index date, hdPS and index date within each population (specific and sensitive).

The main analysis will be performed with the specific NVAF matched cohorts and a grace period of 30 days for the drug discontinuation definition. A secondary analysis will be performed using a statistical adjustment with all specific NVAF subjects, and a grace period of 30 days for the drug discontinuation definition.

The following sensitive analyses will be performed for matched cohorts, as well as all for statistical adjustment with all subjects:

- With a grace period of 60 days for drug discontinuation definition, in order to take into account the drug supply in real life, or short discontinuation and poor drug adherence;
- With the sensitive NVAF subjects and the two grace periods for drug discontinuation definition;
- With unspecified bleeding classified as haemorrhagic stroke for the specific and the sensitive NVAF cohorts.

The following statistical analyses will be performed:

- A flow chart depicting the total number of subjects available in the database, those satisfying the cohort criteria according to the treatment group, and the number of matched subjects for each comparison, and in each population;
- Description of baseline characteristics, three-year history previous the inclusion, follow-up duration for all and matched subjects according to the treatment group, with standardised difference for each comparison;
- Description of drug use patterns including drug MPR for DOAC, dosage, treatment discontinuation, switch to another anticoagulant, co-dispensation of drug predisposing to bleeding and one-year and two-year treatment maintenance for all and matched subjects according to the treatment group, with standardised difference for each comparison;
- Outcomes will be analysed using survival methods for the first occurrence of each outcome:
 - Estimation of the one-year and two-year cumulative incidence of each outcome, and according to individual diagnose of each outcome, during drug exposure for rivaroxaban, dabigatran, and VKA; using Kaplan-Meier estimate for death, cumulative incidence function for clinical outcomes, in order to take into account death as a competing risk.
 - Estimation of the incidence rate (per 100 PY exposed) of each outcome, and according to individual diagnose of each outcome, during drug exposure or if the risk is not constant over the time, during periods with a constant risk.
 - Comparison of the one-year and two-year risk of each outcome during drug exposure: rivaroxaban versus VKA, and rivaroxaban versus dabigatran, using Cox proportional hazard risk model (Cox 1972) for death and Fine and Gray model (Fine 1999) for clinical outcomes in

order to take into account death as a competing risk. Hazard ratio will be presented as point estimate with their 95% confidence interval:

- ✓ Main analysis will compare the incidence of each outcome for matched subjects with adjustment for drugs predisposing to bleeding during drug exposure (time dependant variables).
- ✓ Secondary analysis will compare the incidence of each outcome with all subjects, with adjustment for hdPS and drugs predisposing to bleeding during drug exposure (time dependant variable) for the rivaroxaban versus VKA comparison, and plus low or high DOAC dosage at index date for the rivaroxaban versus dabigatran comparison.
- ✓ Prognostic analysis will be done with all subjects to assess outcome risk factors, including gender, age, CHA2DS2-VASc and HAS-BLED scores, low or high dosage at index date for DOAC, drug predisposing to bleeding during drug exposure (time dependant variable) and significant baseline characteristics. The significant baseline characteristics will be identified firstly with univariate analyses, and therefore using a forward stepwise (taking into account the size of the database, the p threshold will be set at 1/1000 for variables selection and at 5% for the stepwise procedure).
- Estimation of cumulative incidence of each outcome during post-anticoagulant exposure period for rivaroxaban, dabigatran, and VKA (i.e. after anticoagulant discontinuation), using Kaplan-Meier estimate for death, cumulative incidence function for clinical outcomes (stroke and SE, ACS, CRB), in order to take into account death as a competing risk.
- Description of healthcare resources use and cost, for all and matched subjects according to the treatment group rivaroxaban dabigatran, and VKA during the first year of follow-up for all patients, and during two years of follow-up for those included in 2013. Comparison (rivaroxaban versus VKA, and rivaroxaban versus dabigatran) will be done for matched cohorts.

MILESTONES		
Study protocol		Sept-Dec 2015
IDS and CNIL authorisation		Q4 2015-Q3 2016
Development of SAP		Q2-Q3 2016
SNIIRAM data extraction		Q3-Q4 2016
Data management and statistical analysis		Q4 2016-Q1 2017
Final report		Q2 2017

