9.3.3. Exposure

Exposure definitions will use the following variables:

- **VKA** will be defined as B01AA ATC code;
- **DOAC** will be defined as B01AF01 ATC code for rivaroxaban and B01AE07 ATC code for dabigatran;
- **DOAC high dosage** will be defined using CIP codes for rivaroxaban 20mg and dabigatran 150mg;
- **DOAC low dosage** will be defined using CIP codes for rivaroxaban 15mg and dabigatran 110mg;
- **Treatment group** will be defined by the first anticoagulant dispensation during the inclusion period, i.e. rivaroxaban high or low dosage, dabigatran high or low dosage, or VKA;
- **Index date** will be defined as the date of the first dispensation of the anticoagulant in the treatment group;
- **Duration of a drug dispensation** will be defined as the number of daily doses for DOAC and 30 days for VKA;
- **Drug (DOAC or VKA) exposure** will be defined as the period starting at the index date and ending at the date of the last drug dispensation plus the duration of the last drug dispensation for subject with a drug discontinuation (defined below) or at the date of drug switch (defined below), or at the end of follow-up, whichever is the earliest;
- **Drug (DOAC or VKA) discontinuation** will be defined with a grace period of 60 days for the main analysis and 30 days for a sensitive analysis after the last dispensation plus the duration of the last drug dispensation;
- **Drug (DOAC or VKA) switch** defined as a dispensation of another anticoagulant, including heparin and LMWH dispensation (B01AB ATC code), for subject with a drug discontinuation;
- **Post drug (DOAC or VKA) exposure** will be defined as the period starting at date of the end of drug exposure (see above) and ending at the date a new prescription of an anticoagulant or at the end of follow-up, whichever is the earliest;
- **DOAC compliance** will be estimated using Medication Possession Ratio (MPR) during drug exposure defined by the number of defined daily doses dispensed, divided by the number of days of drug exposure for DOAC. Considering the variable dosage of VKA between subjects and over time in individual subjects, no defined daily dose can be defined, and therefore no MPR for VKA exposure.
- During a hospitalisation, drugs are provided by the hospital, and this time will be taken into account for calculation of drug exposure and drug discontinuation.

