9.4. DATA SOURCES

The SNIIRAM database is the national healthcare insurance system database linked to the national hospital-discharge summary database (*Programme de Médicalisation des Systèmes d'Information*, PMSI) and the national death registry, using a unique pseudonymized identifier. It includes the three main healthcare insurance funds (CNAMTS³, MSA⁴, RSI⁵), which represent about 96% of the French population, and currently some of the 19 other smaller French healthcare insurances for specific professional organisations such as militaries, deputies and senators, priests, Opera... (Moulis 2015). To the extent that the SNIIRAM is a national database, all subjects are followed-up until they died. The only dropouts are subjects who leave the country to live abroad and those who join one of the smaller French healthcare insurance organisations not yet included in the SNIIRAM, which is rare and not linked with a disease or healthcare package. The SNIIRAM contains individual pseudonymised information on (Tuppin 2010, Moulis 2015):

- General characteristics: gender, year of birth, affiliation scheme, area of residence;
- Month and year of death;
- Long-term disease (LTD, or ALD in French, and associated ICD-10 codes) with starting and ending date. There is a list of 30 LTD for a total of 3448 available ICD-10 codes, which includes most of chronic diseases with long term and/or expensive treatment; e.g. a disease such as AF is specified by the ICD-10 code within LTD. Registration with a LTD is obtained at the request of a patient's general practitioner and must be validated by the health insurance system physician. Once registered, patients receive full (i.e. 100%) reimbursement for expenditure related to the LTD, as defined by the health authorities. The LTD information is specific for the diagnosis (very low risk of false positives), but not sensitive because not all patients with the disease ask to benefit from a LTD;
- Outpatient reimbursed healthcare expenditures: visits, medical procedures, medical imageries, lab tests, drugs, medical devices, transports, sick leaves... with prescriber and professional caregiver information (medical or paramedical specialty, private/public practice), dates (prescription and dispensation), and codes (but not the medical indication nor result);

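### The off-drug period is set to end at a new prescription while the other exposure boundaries use dispensations; read literally, this misdates restarts in one secondary, descriptive estimate

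*Protocol*

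**What the plan says.** Section 9.3.3 (Exposure) starts post-drug exposure at the end of drug exposure and has it "ending at the date a new prescription of an anticoagulant or at the end of follow-up, whichever is the earliest". The abstract gives the same rule, "Period starting at date of the end of drug exposure and ending at the date a new prescription of an anticoagulant" or at end of follow-up, so this is not shorthand that the body corrects.

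The neighbouring boundaries use a different event:

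- The index date is the "Date of the first dispensation of anticoagulant in the treatment group".
- Drug exposure ends at the last dispensation plus its duration, counted as "the number of daily doses for DOAC and 30 days for VKA", or "at the date of another anticoagulant dispensation (switch) or at the end of follow-up, whichever is the earliest".
- Discontinuation is declared after a grace period that runs from the end of the last dispensation's supply.
- A switch is a "Dispensation of another anticoagulant, including heparin and LMWH dispensation for subject with a drug discontinuation".

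Section 9.4 says that outpatient claims carry "dates (prescription and dispensation), and codes (but not the medical indication nor result"). The two dates are therefore distinct items in the database.

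The period feeds one analysis. Section 9.7.1 (Outcomes) plans the cumulative incidence of each outcome after discontinuation, by drug, to serve a secondary objective in section 8.

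**The concern.** A new prescription and the next dispensation need not fall on the same day. A patient who stops for longer than the grace period and then collects more drug under a prescription written before the stop has a dispensation but no new prescription. Under the stated rule the off-drug clock keeps running after that restart. No other rule stops it, and none returns the patient to drug exposure. Treated days, and any event on them, are then reported as off drug.

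The error can also run the other way. If a new prescription is written some days before it is filled, the off-drug period closes while the patient is still untreated, and events in that interval are lost.

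What is at stake is the meaning of the post-discontinuation incidence. Treated time mixed into it would tend to dilute the off-drug stroke risk and to add bleeds that occurred on treatment.

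**Working it through.** The protocol gives no figure for this, so there is nothing to reproduce. The check has three parts.

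**1. The definitions side by side**

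| Boundary | Event used | Where |
|---|---|---|
| Index date | dispensation | Abstract; 9.3.3 |
| End of exposure, discontinuation | last dispensation plus its duration | Abstract; 9.3.3 |
| End of exposure, switch | dispensation of another anticoagulant | Abstract; 9.3.3 |
| End of post-drug exposure | new prescription | Abstract; 9.3.3 |

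One boundary differs. The protocol also uses the prescription date in its proper sense elsewhere: section 9.3.6 identifies AF-related visits by matching them to the date on which drugs or tests were prescribed.

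**2. A worked timeline** (fill and prescription days are assumed)

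The last VKA fill is on day 0 with 30 days of supply, so exposure ends on day 30. The grace limits are day 30 + 30 = 60 and day 30 + 60 = 90. The patient refills an existing prescription on day 100, past both limits.

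| Period ends at | Counted off-drug days | Days after the restart | Share |
|---|---|---|---|
| Dispensation, day 100 | 100 − 30 = 70 | 0 | 0% |
| New prescription, day 130 | 130 − 30 = 100 | 130 − 100 = 30 | 30% |
| New prescription, day 190 | 190 − 30 = 160 | 190 − 100 = 90 | 56% |
| None before day 730 | 730 − 30 = 700 | 730 − 100 = 630 | 90% |

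In the other direction, a prescription written on day 93 and filled on day 100 gives 93 − 30 = 63 days instead of 70, so 7 untreated days are lost.

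These are single patients. They show the mechanism and not the average effect.

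**3. Average effect under stated assumptions**

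None of these inputs is in the documents, apart from the two grace periods:

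- remaining prescription validity R at the stop is uniform between 0 and 3, 6 or 12 months;
- 20-50% of stoppers restart within 12 months, with exponential time to restart once the gap has passed;
- remaining follow-up F is uniform from 3 to 20 months;
- there are 400,000 simulated stoppers per setting.

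With restart time T, the correct period is min(T, F). If T < R, the literal rule gives min(R, F). Misplaced share = (literal total − correct total) / literal total.

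| Prescription length | 30-day gap | 60-day gap |
|---|---|---|
| 3 months | 0.1-0.3% | 0.01-0.04% |
| 6 months | 0.6-2.1% | 0.3-1.0% |
| 12 months | 2.5-8.0% | 1.8-5.7% |

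In the worst cell (12 months, 50% restart), about 21% of stoppers have a period that ends late with a 30-day gap and about 18% with 60 days. If the 12-month restart share is counted from the end of exposure instead of from the end of the gap, the 30-day upper ends become 2.3% (6 months) and about 9% (12 months).

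Both gaps are shown because the protocol conflicts with itself. Section 9.3.3 gives "a grace period of 60 days for the main analysis and 30 days for a sensitive analysis", while section 9.7.1 (Generalities) gives the reverse. That is a separate matter to be reconciled.

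In terms of a rate, take an assumed 4.0 per 100 person-years off drug and 1.6 on drug (the stroke and SE rate from the earlier VKA study in section 9.5). At 8.0% misplaced time, the off-drug rate reads 0.92 × 4.0 + 0.08 × 1.6 = 3.81. At 0.1% it reads 4.00.

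**The case against.** The strongest reply is that prescription is loose wording here. The definition of probable AF speaks of co-prescription in what can only be claims data, section 9.9 says exposure is assessed from drug claims, and a prescription is visible in this database only through a reimbursed claim. With every neighbouring boundary on dispensations, the authors may well have meant the next anticoagulant claim. Section 9.6 also leaves the detail of exposure definitions to the SAP.

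Much of this stands. A reader might infer that the study will in fact count treated patients as off drug. The documents do not establish that; it follows only if the rule is programmed as written. But no passage says that a new prescription means the next dispensation, and both dates are available to the programmer. Deferring detail to the SAP does not change a boundary event that the protocol already names.

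Two further inferences are tempting and unsupported. One is that the three drugs would be described unequally. That requires restart or refill habits that differ by drug, and the protocol gives none. The other is that the main results are at risk. The hazard ratios in section 9.7.1 (Outcomes) are estimated during drug exposure, which this boundary does not touch, and the post-discontinuation analysis is estimation only, with no comparison between drugs.

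**Conclusion.** The point holds as a minor inconsistency. Followed literally, the rule can end the off-drug period too late for patients who refill an existing prescription and too early for those whose prescription precedes the fill.

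The effect is confined to one secondary, descriptive set of estimates. The percentages above rest wholly on assumed prescription length, restart frequency and follow-up, and they count only the late-ending error. On those assumptions the misplaced share runs from near zero to about 2% of off-drug time for 3-6 month prescriptions. It reaches several percent only if prescriptions run 12 months, which no passage supports, and it is smaller with a 60-day than with a 30-day grace period.

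**What to change.** In the abstract and in section 9.3.3, end post-drug exposure at the date of the first dispensation of any anticoagulant (VKA, any DOAC, heparin or LMWH) on or after the end of drug exposure, or at end of follow-up, whichever is earlier.

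The words on or after matter. A switcher's exposure ends on the date of the switch dispensation. If the rule said only after, the period would run to that patient's second fill and count time on the new drug as off drug. With on or after, such a patient contributes no off-drug time.

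The cost is one clause in two places. Dispensation dates already drive the other exposure rules, so no further data are needed, and the change can be made before the extraction planned for Q3-Q4 2016.
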